3.2 Statistical Analysis Issues

Every effort will be made by the Data Coordinating Center (DCC) to ensure complete, accurate, and high-quality data collection and annotation. However, as with all clinical trials, challenges are anticipated. Given the high mortality rate in this population, missing data is a key issue that may affect both primary and secondary endpoints (e.g., CMV reactivation [missing viral load values], organ dysfunction, and outcomes from the NHLBI-endorsed acute respiratory failure core measurement set). This section outlines the anticipated sources of missing data and corresponding mitigation strategies, informed by experience from the GRAIL Phase 2 trial.

Missing Data in Primary Outcome

Missingness in the primary outcome, RSFDs, is expected to be minimal (~2%) and is likely to be missing not at random (MNAR), primarily due to participant withdrawal of consent. Such withdrawals typically occur in more severely ill participants under high stress. Given the low expected frequency, missing data in RSFDs will be excluded from the primary analysis without imputation.

Missing Data in Some Secondary/Exploratory Outcomes Due to Study Design

Some secondary endpoints (e.g., static respiratory compliance) may be unavailable due to early extubation, ICU discharge, or death prior to scheduled biospecimen collection. For instance, if ganciclovir reduces respiratory support duration, extubated participants may not be eligible for endotracheal aspirates, potentially biasing the analysis. To minimize missingness, biospecimen collection was scheduled at Day 7 (± 1 day), when approximately 40% of participants are expected to remain alive and intubated. If missing data persist despite this timing, we will apply imputation techniques such as last observation carried forward (LOCF), multiple imputation (MI), or conduct sensitivity analyses. If missingness remains substantial, limitations will be acknowledged in interpreting results.

Missing Data in Covariates

Missing covariate data may result from death, withdrawal, or other causes. If covariate missingness exceeds 5%, it will be addressed analytically. Covariate missingness is expected to be MAR, and will be handled using either inverse probability weighting (IPW) or multiple imputation (MI) [1, 2].

- Weighting Adjustments:
 - Estimate the probability of missingness using logistic regression with baseline covariates as predictors.
 - Calculate IPW as the reciprocal of predicted probabilities.

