4. INTERIM ANALYSIS AND DATA MONITORING COMMITTEE

One interim analysis was planned and conducted after 50 deaths. The primary purpose of the interim analysis was to evaluate safety, efficacy, and sample size assumptions. This analysis included an assessment of the primary outcome (RSFDs) and mortality.

The interim analysis was conducted by the unblinded statistical team and reviewed by the independent Data and Safety Monitoring Board (DSMB). Based on pre-specified stopping boundaries and overall risk-benefit assessment, the DSMB recommended continuation of the trial without modification. No additional interim analyses were performed.

DSMB meetings were conducted on the following dates:

DSMB	1/10/2022
DSMB	7/8/2022
DSMB	8/30/2022
DSMB	1/26/2023
DSMB	8/11/2023
DSMB	2/8/2024
Interim Analysis	7/8/2024
DSMB	10/1/2024

The trial was paused for enrollment on July 22, 2022, to allow the DSMB time to review the updated dataset, and enrollment resumed on September 9, 2022. A closed enrollment decision was later made by NHLBI due to safety and futility concerns following the last DSMB meeting on October 1, 2024.

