8. PRIMARY ENDPOINT ANALYSES

The primary endpoint, respiratory-support-free days (RSFDs), is defined as 28 days minus the number of days a participant received respiratory support (including invasive mechanical ventilation, non-invasive ventilation with CPAP or bi-level CPAP and PEEP ≥ 5 cmH₂O, or high-flow nasal cannula oxygen with a flow rate ≥ 30 L/min) through Day 28 following randomization.

- Participants who do not survive through Day 28 will be assigned zero RSFDs.
- Participants who remain on respiratory support on Day 27 will be assigned zero RSFDs.
- Participants transferred to long-term acute care hospitals (LTACHs) will be assigned zero RSFDs.
- Participants who withdrew consent, refused further participation by themselves or a legally authorized representative (LAR), and for whom no further data were collected, or who withdrew due to study closure within the first 28 days will be considered missing for the RSFD endpoint.

RSFDs will be summarized descriptively using the mean, standard deviation, median, and range by treatment group. To formally test the primary hypothesis that the mean difference in RSFDs between treatment arms differs from zero, a two-sample parametric t-test will be used. This test is appropriate even if the normality assumption is mildly violated, given its robustness for moderate sample sizes ($n > 25$). As a confirmatory approach, a two-sample permutation t-test will also be performed. This nonparametric test does not require distributional assumptions and is valid under the weaker condition of exchangeability, which is satisfied in the randomized trial setting.

To further improve statistical efficiency and precision, the semiparametric efficient and robust method of Davidian et al. [7, 8] will be employed to estimate the mean difference between arms, along with its 95% confidence interval. This method adjusts for baseline characteristics predictive of the primary outcome and is more powerful than a conventional ANCOVA or t-test when baseline adjustment is warranted. If data on

the primary endpoint are missing for reasons other than death, the analysis will appropriately account for the missing data mechanism, as described in Protocol Section 6.4.1.

In addition to the ITT analysis, the primary endpoint will also be analyzed in a classical intent-to-treat (cITT) and two modified intent-to-treat (mITT) populations.

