6.4.1 Missing data

Every effort will be dedicated to complete, comprehensive, and accurate data collection and data annotation by the DCC. However, issues and challenges arise in every clinical trial. Due to the high proportion of deaths in this patient population, one major challenge in this RCT of which we must be aware and ready to correct is missing data. Missing data can occur to the primary endpoint and key secondary endpoints (e.g., CMV reactivation [missing viral load values] and organ dysfunction or the NHLBI-endorsed acute respiratory failure core outcome measurement set). We have carefully examined sources of missing data from the GRAIL phase 2 trial and adjusted the analysis plan accordingly.

6.4.1.1 Missing Data in Primary Outcome.

It is highly likely that missing data in RSFDs, the primary outcome in our RCT, will be MNAR (missing not at random), as most missingness will result from withdrawal of consent, a rare occurrence that can happen when patients and families are in crisis, and is more likely to occur in sicker patients. However, we only expect <3% missingness in our primary outcome (see Section 2A), and thus this data can be ignored from the primary analysis. However, if for some unforeseen reasons, missingness in RSFDs does increase beyond a set threshold of 5%, we will have to adjust for it in our analysis plan. In that case, we will use baseline patient characteristics identified in (1) under the Exploratory Objectives/Endpoints (Section 5.3) to model the missing data mechanism in RSFDs, which will be used to estimate the treatment effect unbiasedly using maximum likelihood methods, provided the missing data model is correctly specified.

6.4.1.2 Missing Data in some secondary outcomes due to Study Design.

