7.5 Subject withdrawal

Under certain circumstances, an individual patient must be terminated from participation in this study. Specific events that will result in early termination include:

- Randomized after positive LFA results but prior to negative CLIA-approved ELISA test result,
- Need for respiratory support ends unexpectedly between time of randomization and first study product administration,
- Unexpected death between time of randomization and first study product administration,
- Subject has been inappropriately enrolled based on inclusion/exclusion criteria (e.g. when information through next of kin was inaccurate),
- Site investigator decides to terminate participation for reasons of patient's safety or to prevent compromising the scientific integrity of the study,
- It is determined that side effects are severe,
- New scientific developments indicate that the treatment is not in the patient's best interest,
- Patient or next of kin refuses further participation,
- Study is terminated.

Patients may be withdrawn at any time once the study team becomes aware that the patient meets one or more criteria for withdrawal. If the participant is withdrawn from the study before a dose of study product is given, no study procedures will be performed, no study data will be collected, and they will not be included in the primary analysis population. If a participant is withdrawn after receipt of study product, safety procedures (e.g. monitoring of creatinine and CBC with differential) will continue for another 48 hours, no further study biosamples will be obtained, study data in the medical record will continue to be collected per protocol and as allowed in the signed consent (e.g. respiratory-support-free days), and they will be included in the primary analysis population.

In the event that a participant does not start receiving first dose of study product within 120 hours after hospitalization, and this is discovered before 5 doses of study drug are administered, they must be withdrawn. In this circumstance, no further study procedures will be performed, no further study data will be collected, and they will not be included in the primary analysis population. If initiation of study drug past the 120-hour window is discovered after 5 or more doses of study drug have been given, the participant may remain in the study.

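### SAP 8 makes RSFDs missing for anyone withdrawn at study closure before day 28 but scores earlier death or LTACH transfer as zero, contrary to SAP 3.1 and protocol 7.5

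*SAP*

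**What the plan says.** SAP section 8 lists the scoring rules for the primary endpoint. Two give zero at once: "Participants who do not survive through Day 28 will be assigned zero RSFDs" and "Participants transferred to long-term acute care hospitals (LTACHs) will be assigned zero RSFDs". A third gives a missing value to two groups. One is participants who withdrew consent or refused further participation and have no later data. The other is those "who withdrew due to study closure within the first 28 days will be considered missing for the RSFD endpoint". The condition about absent data is attached to the first group only. SAP 3.2 then states that "missing data in RSFDs will be excluded from the primary analysis without imputation".

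SAP 4 reports that "A closed enrollment decision was later made by NHLBI due to safety and futility concerns", following the DSMB meeting of 1 October 2024. It does not say that follow-up stopped or that anyone was withdrawn.

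Protocol 7.5 lists termination of the study among the reasons for withdrawal. For anyone withdrawn after a dose, it says that "study data in the medical record will continue to be collected per protocol and as allowed in the signed consent", gives RSFDs as its example, and keeps the participant in the primary analysis population. SAP 3.1 says much the same. The endpoint definition in protocol 6.1.1 has no closure rule, and SAP 12 does not list one as a change from the protocol.

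**The concern.** Under the last-off definition, an RSFD count above zero cannot be known until day 28. A zero from death or LTACH transfer is fixed on the day it happens. A rule that stops the clock at closure and deletes whatever is undecided therefore keeps bad outcomes and discards the rest. Whether a value is missing depends on the outcome.

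The rules also collide. A participant withdrawn at closure who dies by day 28 fits both the missing rule and the zero rule, and SAP 8 gives no precedence. Such a death could come to light, because protocol 9.11 allows vital status to be taken from death registry records.

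At stake are a downward pull on both arm means, an unequal pull if early mortality differs between arms, and extra missingness that SAP 3.2 did not consider when it expected about 2%, mainly from withdrawal of consent. Closure was attributed partly to safety, so unequal early mortality cannot be set aside in advance.

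**Working it through.** **Scale.** The plan's own figure reproduces. For a difference of 2.74 days, SD 9.4, two-sided 5% and 85% power, the two-sample t calculation gives 212.3, so 213 per arm and 426 in total (SAP 2.5). With 250 per arm the standard error of the difference is 9.4 × √(2/250) = 0.84 days.

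**Who enters.** Take participants whose day 28 falls after closure and who, if not already dead, are withdrawn at closure. Assume follow-up at closure is uniform on 0 to 28 days and the hazard of death is constant. With 28-day mortality q and L = −ln(1 − q), the share dead before closure is f = 1 − (1 − e^(−L))/L = 1 − q/L.

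- q = 20% (the control-arm assumption in SAP 2.5): L = 0.223, f = 10.4%.
- q = 30%: L = 0.357, f = 15.9%.
- Over q = 10% to 35%, f runs from 5% to 19%. If all the hazard falls in the first 14 days, it runs from 8% to 27%.

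These participants enter as zero. The rest are dropped, apart from LTACH transfers, which SAP 8 also scores zero. Nobody in this group can enter with a positive value.

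**Effect on one arm mean.** Assume N = 240 per arm and a mean of μ = 16.5 days (close to the Phase 2 control-arm VFD mean of 16.33 in protocol Table 6-1). Let k be the number of late participants and d = 10% the share dead before closure. Those dropped number k(1 − d). Their mean is μ/(1 − d) = 16.5/0.9 = 18.3, because some of them would still have died by day 28. The shift is −μkd / (N − k(1 − d)).

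- k = 4: −16.5 × 0.4/236.4 = −0.03 days.
- k = 8: −16.5 × 0.8/232.8 = −0.06 days.

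The values lost are 3.6/240 = 1.5% and 7.2/240 = 3.0% of the arm, on top of the expected 2% or so.

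**Effect on the difference.** Assume 250 per arm, mortality 20% against 30%, and a survivor mean of 20 days in both arms. The true means are 16.00 and 14.00, a difference of −2.00. With m late participants, the analysed mean is the true mean × (250 − m)/(250 − m + m·f).

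| Late per arm | Mean, 20% mortality | Mean, 30% mortality | Difference | Overstated by | Added missingness |
|---|---|---|---|---|---|
| 8 | 242 × 16/242.83 = 15.95 | 242 × 14/243.27 = 13.93 | −2.02 | 0.02 | 2.8% |
| 20 | 230 × 16/232.07 = 15.86 | 230 × 14/233.18 = 13.81 | −2.05 | 0.05 | 6.9% |

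An outer case of 30 late participants in arms of only 135 gives an overstatement of about 0.15 days.

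**Type I error.** With 20% mortality in both arms, simulated rejection rates (6,000 runs each) were 0.052 with 8 late per arm and 0.049 with 20. There is no inflation.

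**Do the other planned analyses repair it?** The permutation test uses the same values. The first mITT set removes those withdrawn after dosing but keeps those who died first, which is the same asymmetry. The second mITT set conditions on survival to day 28. The semiparametric analysis refers to protocol 6.4.1, which acts only if "missingness in RSFDs does increase beyond a set threshold of 5%, we will have to adjust for it" and then models missingness from baseline characteristics. Here missingness depends on randomization date and early outcome, so the repair is not clear.

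**The case against.** The strongest reply is that the documents do not show the rule was ever used. A reader might infer that the last-enrolled patients as a whole enter the analysis only if they did badly. The documents do not support that. SAP 4 reports closure of enrollment, and SAP 8 covers only those withdrawn because of closure. A late enrollee followed to day 28 is scored like anyone else, and the SAP still plans mortality analyses through day 180. This stands, and it limits the point to those actually withdrawn.

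Second, read with SAP 3.1, the clause in SAP 8 may have been meant only for participants without day-28 data. That is possible, but it is not what the sentence says, and one clarifying phrase would settle it. Even on that reading, if records really ended at closure, early deaths would still count and the others would be lost.

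Third, it would be too strong to say that the rule throws away data known to exist. Protocol 7.5 limits collection to what consent allows, and SAP 3.1 to what the record holds. This also stands.

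Fourth, the effect is small. A larger fall of about 0.13 days in an arm mean appears if every dropped participant is treated as a day-28 survivor (mean 16.5/0.8 = 20.6, with k = 8). That is wrong, because some of them would have died between closure and day 28.

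**Conclusion.** The point holds as an inconsistency within the SAP and with the protocol, with an outcome-dependent missing-data rule as its consequence. The selection follows from the scoring rules alone. Its size does not, since the number affected is not given and may be few or none.

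Under the assumed values, the arm means fall by about 0.03 to 0.06 days. If mortality differs as assumed, the difference is overstated by about 0.02 to 0.05 days, roughly 2% to 6% of its standard error and under 2% of the 2.74-day target. The late-cohort sizes, mortality contrast, survivor mean and uniform follow-up are all assumptions.

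A reader might infer a false-positive problem or a bias towards a particular arm. Neither is supported: type I error stays near 5% when the arms are alike, and the documents give no mortality by arm. The change is worth making because it removes a contradiction in the primary endpoint at little cost.

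**What to change.** Amend SAP 8 to agree with SAP 3.1 and protocol 7.5. Score dosed participants withdrawn because of study closure from the medical record through day 28 wherever consent and records allow. Use missing only when no record data can be obtained. State which rule takes precedence when a participant withdrawn at closure is known to have died by day 28.

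Report, by arm, how many participants were withdrawn at closure before day 28, how many of these were scored from the record, and how many remain missing. Add one sensitivity analysis that omits everyone randomized fewer than 28 days before closure, whatever their outcome. Membership then depends on calendar date and not on outcome.

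The cost is a few words in the SAP, chart completion for the participants affected, and one extra analysis.

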9. SAFETY ANALYSES

A summary table of MedDRA-coded adverse events (AEs) will be generated, displaying the frequency and percentage of participants experiencing each AE by treatment group, system organ class (SOC), and preferred term. In addition, a comprehensive listing of all reported AEs will be provided. This listing will include onset date, verbatim term, MedDRA code, SAE/EAE classification, study day, severity grade, relationship to study drug, outcome, and duration (in days).

Deaths will be summarized separately by treatment group, as described in Section 2.2. A Kaplan–Meier survival analysis will be conducted to estimate the time-to-death distribution for each arm. Survival curves will be compared using the log-rank test. A Cox proportional hazards model will also be used to estimate the hazard ratio (HR) and 95% confidence interval (CI) for mortality between groups, adjusting for baseline creatinine clearance. In addition, subgroup analyses will be conducted stratified by baseline creatinine clearance (≥ 60 vs. < 60 mL/min).

Survival analyses will be performed across multiple time windows: through Day 28 and Day 180 (± 42 days). Participants lost to follow-up will be censored at their last known survival date.

To further explore potential differences in mortality risk across treatment phases, an interaction analysis will be conducted between treatment assignment and treatment period (during-treatment vs. post-treatment). This analysis will help assess whether the effect of treatment on mortality differs between the period of active drug administration and the post-treatment period.

